Prompt and adequate treatment for infection during pregnancy is vital given the well-established association between maternal infection during pregnancy and adverse birth outcomes, including miscarriage and stillbirth.(17) More evidence is needed on whether there is a causal association between maternal macrolide antibiotics treatment during pregnancy and adverse child outcomes.

2. Objectives

We will conduct a population-based cohort study to evaluate the association between the macrolide antibiotics prescription in pregnancy and adverse child outcomes (neurodevelopmental disorders and major malformation (overall and system-specific)) (**primary analysis**), and to examine this association by macrolides subtypes and length of prescriptions (**subgroup analysis**).

3. Data source

We will use the Clinical Practice Research Datalink (CPRD), a UK-representative database which captures prospective, anonymised data on prescriptions, diagnoses, and symptoms records in primary care.(18) A Mother-baby link was built within CPRD using family ID, practice ID, and date of birth/delivery, with details reported elsewhere.(19, 20) For each mother-baby pair, a delivery date was estimated (Appendix).

4. Methods

4.1 Study design

Retrospective cohort study with prospectively collected data.

4.2 Study Population

The Mother-baby link includes 1,071,379 children born from Jan 1st 1990 to June 30th 2016.

Inclusion Criteria:

- Children whose mother was prescribed an only monotherapy of macrolide or penicillin during pregnancy (between 5 Gestational Week [GW] and delivery)
- Children who registered with the general practice (GP) within 6 months of birth
- Children whose mother was aged 14 to 50 years at delivery and had been registered with GP from at least 50 weeks before estimated conception date to delivery

Exclusion Criteria:

Children with known chromosomal abnormalities or with fetal exposure to known teratogenic medications (warfarin, angiotensin-converting enzyme (ACE) inhibitors, antineoplastic agents, isotretinoin, misoprostol, and thalidomide).

Children will be followed from birth to death, end of follow-up (June 30th, 2016), or age 14, whichever came first.

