4.3 Study Variables

4.3.1 Exposure

The exposure group will include children whose mother were prescribed an only monotherapy of macrolide antibiotics from 5 GW to delivery (hereafter, “during pregnancy”). A monotherapy is defined as one or more consecutive prescriptions for a single antibiotic (i.e. same drug substance) separated by no more than 30 days and uninterrupted by prescriptions for other antibiotic drug substances. The macrolides prescription is identified using a drug code list based on chapter 5.1.5 of the British National Formulary. The date of first prescription is used as the index date. The reference group includes children whose mothers were exposed to an only monotherapy of penicillins during pregnancy. Preliminary analysis shows that 81% of all antibiotic prescriptions were monotherapies. We further divide the time window into 1) 5GW to 13GW (29 Gestational Day [GD] to 91GD, hereafter, “1st trimester”), the critical period for most major malformation, and 2) 14GW to delivery (hereafter, “2nd–3rd trimester”).(21) The negative control cohort (see “4.4.2 Sensitivity analyses [1]”) includes children of mothers prescribed an only monotherapy of macrolides or penicillins during 10-50 weeks prior to conception and are not included in the study cohort.

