Appendix

A hierarchy of available pregnancy markers was chosen that reflects their potential accuracy to estimate start of the pregnancy episode. Pregnancy markers that directly provide gestational age such as gestational age in weeks, prenatal examination, and fertility procedures (IVF) were on the top of the hierarchy. Next hierarchy of markers include ranges of gestational week indicators (e.g. premature 24-26 weeks) and outcome-specific estimates (e.g. premature labour, imputed as 36 weeks, because around 60% live premature births born at 36 gestational weeks). Gestational weeks imputed from birthweight was on the 3rd hierarchy, based on the intrauterine growth curves published by Irene E. Olsen et al.(32) For pregnancies with no information available for the above three hierarchies of markers, full term births were assumed and gestational week 40 were used to calculate pregnancy start dates. Codes used in each hierarchy is referenced from Matcho, A. et al. (33)

For babies in the Mother-baby link, gestational age were measured from each hierarchy with the following proportion: 27.8% from the first hierarchy (from codes for gestational age), 14.3% from the second hierarchy (from codes for gestational week range), 8.2% from the third hierarchy (imputed based on birthweight), 49.6% (imputed as full term, 40 gestational weeks). The proportion of preterm birth was 6.2% preterm births in general populations, which is marginally lower than reported by the Office for National Statistics (7.1%).(34) The potentially underestimated proportion of preterm births would over-record antibiotic exposure during the early pregnancy, which would bias the association towards null.

Reference

1. Agency MHPR. Package leaflet: Information for the user: Clarithromycin 250 mg Film-Coated Tablets 2016 [Available from: <http://www.mhra.gov.uk/home/groups/spcpil/documents/spcpil/con1507872162573.pdf>.
2. Britain; JFCG. British National Formulary. Pharmaceutical Press; 2016. p. 307.

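### Antibiotic courses issued just before gestational day 29 are ignored, so some pregnancies enter the wrong arm or pass as single-drug; the expected effect is small and one look-back rule closes the gap

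*Combined protocol and SAP*

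**What the plan says.** - **Eligibility (4.2).** The mother must have been "prescribed an only monotherapy of macrolide or penicillin during pregnancy (between 5 Gestational Week [GW] and delivery". She must also have been registered with the practice from at least 50 weeks before conception.
- **Exposure window (4.3.1).** The macrolide arm is "prescribed an only monotherapy of macrolide antibiotics from 5 GW to delivery (hereafter, “during pregnancy", so the plan's term for pregnancy exposure leaves out the earlier gestational days. The window opens on GD 29. The comparator uses the same window: "The reference group includes children whose mothers were exposed to an only monotherapy of penicillins during pregnancy".
- **Monotherapy (4.3.1).** A course is "one or more consecutive prescriptions for a single antibiotic (i.e. same drug substance) separated by no more than 30 days and uninterrupted by prescriptions" of another antibiotic substance. On timing, "The date of first prescription is used as the index date". No condition on earlier antibiotic use is attached to either sentence.
- **Elsewhere.** Prior antibiotic use is not in the covariate list (4.3.3). None of the four sensitivity analyses (4.4.2) examines it in the study cohort. The only pre-pregnancy antibiotic window, "an only monotherapy of macrolides or penicillins during 10-50 weeks prior to conception", defines the separate negative control cohort.

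**The concern.** Whether a pregnancy counts as single-drug is judged on prescriptions dated from GD 29 onwards. A prescription dated a few days earlier does not count, even when the tablets are still being taken on GD 29. Two kinds of pregnancy are then labelled in a way that does not match the idea behind the rule.

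- **Macrolide before, penicillin later.** Take a 7-day macrolide course issued on GD 27, which runs to GD 33, and one penicillin course at 20 weeks. The child enters the penicillin reference group although the fetus was exposed to the study drug inside what the plan treats as the critical period for malformations. This mainly affects the whole-pregnancy and 14-weeks-to-delivery analyses.
- **Another antibiotic before, macrolide just after.** Take penicillin on GD 26 and a macrolide on GD 30. The child enters as macrolide-only. Had the penicillin been issued on GD 30 and the macrolide on GD 34, the pregnancy would have been excluded as not single-drug. This mainly affects the 5–13 week analysis.

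There is also an ambiguity. If the same substance is issued shortly before GD 29 and again after it, the 30-day gap joins the two prescriptions into one run. The plan does not say whether that run, and its index date, then starts before the window.

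At stake are the purity of the two arms at the lower edge of the window and consistent treatment of switchers.

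**Working it through.** The plan gives no figure for antibiotic use just before GD 29, so there is none to reproduce on this point. The size has to be built from its counts.

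**Inputs.** About 10,000 macrolide and 100,000 penicillin pregnancies (4.5). 1,071,379 births in the Mother-baby link (4.2). Window GD 29 to 280 for a 40-week pregnancy, which is 252 days. Look-back of 30 days, the plan's own episode gap. Assumptions: prescribing in those 30 days runs at the in-window daily rate, and courses are independent.

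**1. Macrolide in the 30 days before GD 29, among penicillin mothers.**
- Macrolide share of births: 10,000 / 1,071,379 = 0.93%.
- In 30 days: 0.93% × 30/252 = 0.11%, about 110 of 100,000.
- The plan's counts cover only single-course pregnancies, so the true rate may be higher. With an assumed 30% of mothers prescribed either class, split 1:10 as in 4.5: 30% × 1/11 × 30/252 = 0.32%.

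**2. Of these, courses that actually reach GD 29.**
- A 14-day course must be issued on GD 16–28 (13 days): 0.93% × 13/252 = 0.05%.
- A 7-day course must be issued on GD 23–28 (6 days): 0.93% × 6/252 = 0.02%.

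**3. Dilution.** If a share c of the reference group carries the macrolide risk and the true risk ratio (RR) is 2, the reference risk p becomes p(1 − c) + 2pc = p(1 + c), and the observed RR is 2/(1 + c).

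| c | Observed RR |
|---|---|
| 0.11% | 1.998 |
| 0.32% | 1.994 |
| 1% (assumed, about nine times 0.11%) | 1.98 |
| 5% (assumed) | 1.90 |

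**4. Switchers into the macrolide arm.** No document figure gives the rate of switching across GD 29. Independence is the wrong model for a switch, so no estimate is offered.

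**5. Cohort lost to a 30-day look-back.**
- Either class, plan's counts: 110,000 / 1,071,379 = 10.3%; × 30/252 = 1.2%.
- Assumed 30% rate: 30% × 30/252 = 3.6%.

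**6. Effect of that loss on the power rule in 4.5.** With 100,000 penicillin pregnancies, RR 2, two-sided 5% and 80% power, the arcsine method requires 6,046 macrolide pregnancies at baseline risk 0.002 and 12,892 at 0.001. This agrees with Table 2, which includes the first and excludes the second. At baseline risk 0.002 and 10,000 macrolide pregnancies, power is 94.3%. Removing 5% of both arms, more than the loss estimated above, leaves 93.2%.

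**The case against.** **The monotherapy sentence is not limited to the window.** If courses were built on the full prescription record and only then placed in time, a run crossing GD 29 could be recognised. That is possible, but the plan does not say so, and it would settle only the same-substance case. The condition "separated by no more than 30 days and uninterrupted by prescriptions for other antibiotic drug substances" covers other drugs within a run. A different drug issued before the run does not interrupt it, so both examples survive.

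**Switchers are correctly classed as macrolide-exposed.** This stands. The macrolide was issued inside the window. What remains is an inconsistency with how the plan treats the same switch a few days later, and possible confounding. A reader might infer that these women had more severe infections and so bias the macrolide arm towards harm. The documents give neither severity data nor a switching rate, so neither direction nor size can be claimed. The analysis restricted to respiratory infection deals partly with indication, not with severity, and does not remove switchers.

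**The contamination is tiny.** This also stands, under independence. Clustering of courses within women would raise it, but the documents give no rate.

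**Other inferences that go too far.** Index dates on GD 29–58 make up 30 of the 63 days in the 5–13 week window, or 48%. That is the span in which a problem is possible, not a share of pregnancies affected. The 10-week buffer in the negative control cohort keeps control exposure away from pregnancy and is not evidence that a washout was forgotten. Nor are earlier prescriptions invisible: the registration requirement means the records exist, and the rule simply does not use them.

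**A look-back tied to GD 29 is poorly aimed.** It would also remove a woman with an antibiotic shortly before GD 29 and one unrelated course at 35 weeks. True, but a look-back tied to the index date would miss the macrolide-then-later-penicillin case, which is the actual misclassification.

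**Conclusion.** The gap is real on the plain wording and nothing elsewhere in the plan closes it. It puts a small number of macrolide-exposed fetuses in the reference group and treats switchers differently on either side of GD 29. The expected dilution is slight: about 0.1% to 0.3% of the penicillin arm, taking a true RR of 2 to about 1.99. This rests on independence, on a constant daily prescribing rate and, for the upper figure, on the assumed 30%. The effect of switchers on the 5–13 week analysis cannot be sized from the documents and could go either way.

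The documents do not support a claim that the first-trimester results are substantially contaminated or that the power decisions in Table 2 are undermined. The case for changing the rule is consistent exposure classification at very low cost.

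**What to change.** In 4.2 and 4.3.1, for both arms:

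1. State that antibiotic courses are built on the full prescription record, and how a run crossing GD 29 is handled.
2. Exclude children whose mother had any systemic antibiotic prescription in the 30 days before GD 29. This uses the plan's own episode gap, and it removes courses that cross the boundary instead of giving them an index date inside the window.
3. Report the number excluded by arm, which supplies the rate that the documents lack.
4. Keep the current rule as a sensitivity analysis.

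**Cost.** One eligibility rule and one extra run. The 50-week registration requirement already guarantees the data. The expected loss is roughly 1–4% of the cohort under the assumptions above, with little effect on power.

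**Limit.** The boundary stays imprecise where gestational age is imputed, "49.6% (imputed as full term, 40 gestational weeks" according to the Appendix. For example, if such a birth was truly at 41 weeks, true GD 29–35 is labelled GD 22–28. The look-back would catch antibiotics issued in those days, but it cannot correct the dating.

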4.3.2 Outcome

Based on previous evidence from experimental and epidemiological studies, we hypothesized that short-term fetal hypoxia induced by fetal arrhythmia could possibly be the underlying mechanism of observed adverse effects of macrolides.(22) We therefore include outcomes which could potentially result from short-term fetal hypoxia, i.e. neurodevelopmental disorders (CP, epilepsy, attention-deficit/hyperactivity disorder (ADHD) and autism spectrum disorder (ASD)) and major congenital malformation (malformation overall and system-specific malformations).

Neurodevelopmental disorders (CP, epilepsy, ADHD and ASD) are defined as the time to the first Read code or prescription indicating the outcomes by 14 years old. We have identified CP cases from informative prescription or Read codes using the Random Forest approach and were validated by a paediatric-neurologist blinded to the prenatal antibiotics exposure.(23) Other neurodevelopmental disorders (epilepsy, ADHD and ASD) will be identified with previously validated criteria using diagnostic codes and/or prescriptions (table 1). (24-26)

Major malformations will be identified from the European Surveillance of Congenital Anomalies (EUROCAT).(27) We will exclude musculoskeletal malformations (e.g. Club foot, knock-knee and hip dislocation) because they are not reliably recorded in GP records.(28) We also exclude children with known chromosomal abnormalities and children whose mother were exposed to known teratogenic medications (warfarin, angiotensin converting enzyme (ACE) inhibitors, antineoplastic agents, isotretinoin, misoprostol, and thalidomide). Any of the remaining 11 system-specific malformations are defined as major malformation overall, identified from child GP records up to 3 years old using Read codes which are mapped to the tenth edition of the International Classification of Diseases (ICD–10) code lists in EUROCAT (Table 1).(27) Five system-specific malformations (nervous, cardiovascular, digestive, genital tract, and urinary tract) were included which met the power criterion using the EUROCAT prevalence table.(29) (see “4.5 Power analysis”)

Table 1. Outcome identification.

Outcome	Case identification criteria
Cerebral palsy	Method based on predictor selection and prediction (23)
Epilepsy	2 prescriptions of antiepileptic drug (AED, identified based on British National Formula Chapter 4.8) within 4 months or ≥ 1 diagnosis

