4.4 Analyses

4.4.1 Statistical methods

Standardized differences will be used to assess covariate balance between the macrolides group and the penicillins group; meaningful imbalances are defined by an absolute standardized difference of more than 0.1.(30) For neurodevelopmental disorders, absolute rates of outcomes and unadjusted hazard ratios with 95% confidence intervals will be calculated. For malformations, absolute risks of outcomes and unadjusted risk ratios with 95% confidence intervals, will be calculated. Exposure propensity scores will be estimated as the predicted probability of receiving the macrolides prescription (vs. penicillins), conditional on the covariates described above, with the use of logistic-regression models. For each estimated propensity score, the population in the nonoverlapping areas of the propensity-score distributions will be trimmed, and 50 strata will be created on the basis of the distribution of the treated women.(31) Weights for the reference group will be calculated according to the distribution of the treated women among propensity-score strata. We then use the weight to estimate adjusted baseline characteristics, and adjusted hazard ratios (in Cox proportional hazard models with weight statement for neurodevelopmental disorders) or risk ratios (in log-binomial model with weight statement for malformations) as well as their 95% confidence intervals. To account for the clustering of siblings and multiple births within mother, robust standard errors will be estimated. The analyses will be conducted using RStudio version 3.5.1.. No adjustment will be made for multiple comparisons, and results for comparisons of exposure timing and subgroup analysis should be interpreted as exploratory.

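### Follow-up in section 4.2 does not end when a child leaves the practice, so absolute neurodevelopmental rates are understated as written; adjusted hazard ratios shift materially only if leaving still differs after weighting

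*Combined protocol and SAP*

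**What the plan says.** Section 3 describes the data source as one that "captures prospective, anonymised data on prescriptions, diagnoses, and symptoms records in primary care". Section 4.2 takes children "born from Jan 1st 1990 to June 30th 2016" and sets two registration conditions. The mother must have "had been registered with GP from at least 50 weeks before estimated conception date to delivery". The child's condition applies at entry only: "Children who registered with the general practice (GP) within 6 months of birth".

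The end of follow-up is then given as a closed list: "Children will be followed from birth to death, end of follow-up (June 30th, 2016), or age 14, whichever came first". The bracketed date fixes the second item as a calendar date, so it cannot be read as each child's own end of records.

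Section 4.3.2 has neurodevelopmental disorders "defined as the time to the first Read code or prescription indicating the outcomes by 14 years old" and malformations "identified from child GP records up to 3 years old using Read codes". Section 4.4.1 states: "For neurodevelopmental disorders, absolute rates of outcomes and unadjusted hazard ratios with 95% confidence intervals will be calculated". It also plans weighted Cox models for the neurodevelopmental outcomes, and absolute risks with log-binomial risk ratios for malformations. No section mentions transfer out, deregistration or the end of a practice's data supply, and none of the four sensitivity analyses in 4.4.2 is directed at incomplete registration.

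**The concern.** A child is observable only while registered with a contributing practice. If a child leaves at age 4 and would otherwise be followed to 14, the rule as written credits ten further years of event-free follow-up that nobody observed. The consequences differ by estimate.

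- **Absolute neurodevelopmental rates.** The denominator is inflated and the numerator is not, so the rates are too low. This does not depend on any difference between groups.
- **Unadjusted hazard ratios.** These are shifted by any crude difference in leaving between the macrolide and penicillin groups, in either direction.
- **Adjusted hazard ratios.** These are shifted materially only by a difference in leaving that remains after propensity-score weighting.
- **Malformations.** A child coded before leaving is a case. A child with no code and less than three years of records counts as a non-case, so absolute risks are lowered too, though less because the window is short.

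**Working it through.** **Inputs from the documents.** Births from 1 January 1990 to 30 June 2016 (26.5 years); follow-up limited at 30 June 2016 and at age 14; malformation window to age 3. The plan states no person-time and no leaving rate, so it has no figure of its own to reproduce on this point. The Table 2 inclusion decisions are not affected.

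**Assumptions.** Births uniform over the 26.5 years; deaths ignored; children leave at a constant rate r per year, with 3–10% shown; rare events at a constant rate over ages 0–14; nothing recorded after leaving.

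**Step 1: follow-up as written.** The share of children with more than *a* years available before 30 June 2016 is 1 − a/26.5. Mean follow-up is ∫₀¹⁴ (1 − a/26.5) da = 14 − 196/53 = 10.30 years.

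**Step 2: registered follow-up.** I(r) = ∫₀¹⁴ (1 − a/26.5) e^(−ra) da. The rate as written divided by the rate censored at leaving is I(r)/10.30.

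| Leaving per year | I(r), years | Ratio | Rate understated by |
|---|---|---|---|
| 3% | 8.62 | 0.837 | 16% |
| 5% | 7.72 | 0.749 | 25% |
| 8% | 6.60 | 0.641 | 36% |
| 10% | 5.99 | 0.582 | 42% |

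**Step 3: hazard ratios.** For a rare outcome, the recorded hazard is the true hazard times the share still registered. The as-written hazard ratio is therefore multiplied by about I(r₁)/I(r₀), with r₁ for macrolides and r₀ for penicillins.

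| Macrolide v penicillin leaving | Factor |
|---|---|
| equal | 1.000 |
| 6% v 5% | 0.948 |
| 5% v 6% | 1.055 |
| 8% v 6% | 0.903 |

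For the unadjusted ratio the relevant difference is the crude one; for the adjusted ratio it is what remains after weighting. Suppose leaving depends only on a measured covariate (10% per year with it, 4% without; prevalence 50% in the macrolide group, 30% in the penicillin group). With I(0.10) = 5.99 and I(0.04) = 8.15, the unadjusted factor is (0.5 × 5.99 + 0.5 × 8.15)/(0.3 × 5.99 + 0.7 × 8.15) = 7.07/7.50 = 0.94. After weighting it is 1.00.

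**Step 4: check by simulated Cox models.** These used six runs of 1,000,000 v 3,000,000 children at an event rate of 0.0006 per year. With 6% v 5% leaving and a true hazard ratio of 2.00, the estimate is 1.90 as written and 2.00 when censored at leaving. With 5% in both groups it is 1.99 either way. The simulated rate at 5% leaving is 0.000451 as written and 0.000603 when censored, against a true 0.0006.

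**Step 5: malformations.** With h the age span over which first codes are spread evenly, M(r,h) = (1/h) ∫₀ʰ (1 − a/26.5) e^(−ra) da. The loss from leaving alone is 1 − M(r,h)/M(0,h).

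| | Codes spread over ages 0–3 | Codes all in year 1 |
|---|---|---|
| Leaving 3% per year | 4.3% | 1.5% |
| Leaving 5% per year | 7.0% | 2.4% |
| Leaving 10% per year | 13.3% | 4.8% |
| Late birth alone, 1 − M(0,h) | 5.7% | 1.9% |
| Risk-ratio factor, 6% v 5% | 0.986 | 0.995 |

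The late-birth row arises because children born shortly before June 2016 cannot reach age 3. It is separate from the missing leaving rule.

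**The case against.** The strongest reply is that this is an unstated detail with little bearing on the study's purpose. The primary analyses are comparisons of macrolides with penicillins, and absolute rates are secondary output. Both groups received antibiotics and meet the same maternal registration rule. The weighting covers maternal age, birth year, smoking, drug use and chronic conditions, and imbalance above a standardized difference of 0.1 is flagged. At that threshold (34.7% v 30% in the covariate example of Step 3) the factor is 0.986. The negative-control cohort would also show leaving differences tied to maternal characteristics. The analysts may censor at leaving anyway.

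Much of this stands for the adjusted hazard ratios, which is why the claim about them is conditional. Two limits apply. The covariates in 4.3.3 include no practice, region or deprivation variable, so balance in leaving should be checked, not assumed. The negative control is also at most a partial check on the ratios and cannot repair the rates, which section 4.4.1 commits to calculating. If the analysts do censor at leaving, 4.2 misdescribes the analysis.

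A second objection is that 16–42% depends on a constant event rate. That is correct about size. At 5% leaving, recorded events are 0.89 of the true number if onset is confined to ages 0–5 and 0.66 if confined to ages 4–14; the 6% v 5% hazard-ratio factor becomes 0.977 or 0.922. Nor does censoring alone turn a crude rate into the 0–14 average when incidence varies with age: at 5% leaving, the crude censored rate is 0.889/0.749 = 1.19 times that average for onset at 0–5, and 0.660/0.749 = 0.88 times for onset at 4–14. The as-written rate is too low in every case.

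The malformation part is minor for the risk ratios, and the added analysis there is optional.

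**Conclusion.** The concern holds and should be fixed. Section 4.2 gives a closed list of ends of follow-up that, applied exactly, counts unobservable time. The downward direction for absolute neurodevelopmental rates needs only that some children leave and that their later outcomes are not recorded. The size, 16–42%, is illustrative: it rests on assumed leaving of 3–10% per year, uniform births and a constant event rate.

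Unadjusted hazard ratios move with any crude difference in leaving, by about 5% for 6% v 5% per year. Adjusted hazard ratios move materially only if leaving still differs after weighting, and the documents do not indicate that it does. Absolute malformation risks fall by roughly 1.5–13% from leaving, with little effect on risk ratios if leaving is similar in the two groups.

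**What to change.** Amend 4.2 so that follow-up runs from birth to the earliest of death, end of the child's registration with the practice, end of the practice's data supply, 30 June 2016, or age 14. Report registered follow-up by group after weighting, so that readers can see whether leaving is balanced; censoring relies on leaving being unrelated to the outcome once the weights are applied. Because incidence may vary with age, age-banded rates would be easier to compare than one crude rate.

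For malformations, add a secondary analysis of time to first code up to age 3 with the same censoring, which handles both leaving and late birth. Do not instead require three years of actual registration: that drops cases coded before a move and selects on an event after baseline.

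The cost is one sentence and one added analysis. Registration end dates and practice data-supply dates are needed, and the documents do not name these fields. Counted person-time falls from 10.3 to between 8.6 and 6.0 years per child on the assumed leaving rates. No case is lost if nothing is recorded after leaving; the documents do not say so, and any code dated after leaving would be dropped.
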